5.2.2 Subsequent Cycles

- ANC must be $\geq 1000/\text{mm}^3$
- Hemoglobin must be ≥9mg/dl
- Platelets must be $\geq 75,000/\text{mm}^3$
- Serum creatinine ≤1.5 x ULN, or measured creatinine clearance (CrCl) ≥45 mL/min as calculated by the Cockcroft-Gault method or 24-hour measured urine CrCl ≥45mL/min
- Transaminitis must return to \leq grade 2
- Diarrhea must be resolved \leq grade 1.
- Nausea and Vomiting must return to ≤ grade 1
- Neurosensory must be \leq grade 2
- Other Treatment Related non-Hematologic Toxicity must return to ≤ grade 1

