5.5 Criteria for Taking a Participant Off Protocol Therapy

Duration of therapy will depend on individual response, evidence of disease progression and tolerance. In the absence of treatment delays due to adverse event(s), treatment may continue until one of the following criteria applies:

- Disease progression
- Intercurrent illness that prevents further administration of treatment
- Unacceptable adverse event(s)
- Treatment delay of > 21 days due to toxicity
- Participant demonstrates an inability or unwillingness to comply with the medication regimen and/or documentation requirements
- Participant decides to withdraw from the protocol therapy
- General or specific changes in the participant's condition render the participant unacceptable for further treatment in the judgment of the treating investigator

Participants will be removed from the protocol therapy when any of these criteria apply. The reason for removal from protocol therapy, and the date the participant was removed, must be documented in the case report form (CRF) and entered in the Clinical Trial Management System (OnCore). Alternative care options will be discussed with the participant.

In the event of unusual or life-threatening complications, treating investigators must immediately notify [name] MPH at [contact].

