*Participants requiring a delay of >3weeks should discontinue AZD1775.		
**Participants requiring > two dose reductions should discontinue AZD1775.		

Other Non- Hematologic Toxicities	Management/Next Dose for AZD1775	
Grade 1	No change in dose	
Grade 2^	Hold until ≤ Grade 1. Resume at same dose level.	
Grade 3	Hold until < Grade 2. Resume at one dose level lower, if indicated.	
Grade 4	Hold until < Grade 2. Resume at one dose level lower, if indicated.	

- Dose modifications for AZD1775 non-hematologic toxicities should be based on toxicities occurring during the previous cycle.
- For toxicities that lead to a dose reduction, the dose will not be re-escalated during subsequent cycles.
- Any patient who develops a Grade 3 or 4 nonhematologic toxicity that does not resolve to ≤ Grade 1 within 3 weeks should discontinue AZD1775, unless approved by the Principle Investigator.
- Participants requiring > two dose reductions, should discontinue AZD1775.
- ^intolerable Grade 2

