6.2 Dose Delays and Modifications for Cisplatin

Cisplatin will be initially administered at a dosage of 75mg/m² as an IV infusion given every 3 weeks. Patients who experience a Grade 3 or 4 toxicity attributable to cisplatin will have their cisplatin dose reduced to per Table 6-2. Toxicities resulting in myelosuppression, renal insufficiency, ototoxicity, and marked nausea and vomiting are most commonly seen with cisplatin monotherapy. Assessments should be made immediately prior to the scheduled administration of the chemotherapy. If patient needs to discontinue cisplatin therapy, patient can be treated on protocol with AZD1775 monotherapy.

Table 6-2 DOSE MODIFICATION OF CISPLATIN

Dose Level	Cisplatin Dose
0	75mg/m^2
-1	60mg/m^2
-2	50mg/m^2

Dose delays and modifications are summarized in the toxicity table in Table 6-6.

No dose re-escalations are allowed on study, except where noted below.

Expected toxicities for Cisplatin:

Nephrotoxicity

The major dose-limiting toxicity of cisplatin is cumulative nephrotoxicity. Tubular necrosis of both proximal and distal renal tubules has been noted in 28% to 36% of subjects treated with a single dose of 50mg/m^2 . It is first noted during the second week after a dose and is manifested by elevations in BUN and creatinine, serum uric acid and/or a decrease in creatinine clearance. Renal toxicity becomes more prolonged and severe with repeated courses of the drug. Renal function must return to normal before another dose of cisplatin can be given. Nephrotoxicity can be reduced by IV hydration and mannitol diuresis.

Nausea and Vomiting

Cisplatin causes moderate to severe nausea and vomiting in almost all subjects treated. Nausea and vomiting usually begin within 1 to 4 hours after treatment and last up to 24 hours. Various degrees of vomiting, nausea, and/or anorexia may persist for up to 1 week after the treatment. Delayed nausea and vomiting (beginning 24 hours or after chemotherapy) has occurred with complete emetic control on the day of cisplatin therapy. The use of prophylactic and continuing antiemetic medication reduces these adverse effects.

Hypomagnesemia

Hypomagnesemia has been reported in subjects treated with cisplatin and is probably related to renal tubular damage. It may become severe enough to cause tetany. Generally, serum electrolytes return to normal levels when cisplatin is discontinued and supplemental electrolytes are administered.

Ototoxicity

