If GCSF is initiated, then the required dose modification will be adjusted according to the guidelines in footnote of Table 6-3.

Table 6-3
Dose Adjustments for Cisplatin Based on Hematologic Values for Preceding Cycle

Platelets (×1	0 ⁹ /L)	ANC (×10 ⁹ /L)	Dose of Cisplatin
≥75	and	≥1.0	75mg/m ^{2*}
≥50	or	≥ 0.5	60mg/m ^{2*} ,#
< 50	or	<0.5	50mg/m^{2*} ,@
Recurrence of	grade 3 or 4 th	rombocytopenia after 2 dose reductions	Withdraw subject from study
or			continue on ADZ1775
alone			
Recurrence of	grade 3 or 4 ne	utropenia after 2 dose reductions	Withdraw subject from study
or			
			continue on ADZ1775
alone			

^{*} Treatment should be delayed until recovery of platelets to $\geq 100 \times 10^9 / L$ and ANC to $\geq 1.0 \times 10^9 / L$.

Non-Hematologic Toxicity

For other grade 3 or higher non-hematologic effects (with the exception of grade 3 transaminase elevations and nausea or vomiting), treatment should be delayed until resolution (less than or equal to baseline). Treatment can be resumed at 60mg/m², if deemed appropriate by the treating physician, for all subsequent cycles.

Neurosensory Toxicity

[#] For ANC ≥0.5 treat at 75mg/m² dose if initiating GCSF

[@] For ANC<0.5 treat at 60mg/m² dose if initiating GCSF

Adjustments of the cisplatin dose in subjects with neurosensory toxicity are shown in Table 6-4. Cisplatin therapy should be held for grade 2 or higher neurosensory toxicity and should resume with a dose reduction once it has resolved to grade 1.

Table 6-4
Dose Adjustments for Cisplatin Based on Neurosensory Toxicity

CTCAE Grade	Dose of Cisplatin
0-1	100% of previous dose
2	60mg/m^2
3-4	Withdraw participant from study or continue on AZD1775
alone	

Tinnitus or Significant Hearing Loss

In cases of tinnitus or significant hearing loss, cisplatin therapy should be reduced or stopped, at the discretion of the investigator.

Nephrotoxicity

Cisplatin dose adjustments in subjects with renal toxicity are shown in Table 6-5. Either serum creatinine or estimated creatinine clearance may be used. If a dose delay or dose reduction occurs due to nephrotoxicity, subsequent doses of cisplatin may be escalated based on the renal function on the day of treatment (+/- 3 days) and should be determined based on Table 6-5.

Table 6-5
Cisplatin Dose Adjustments for Renal Toxicity

Creatinine(mg/dl)	OR Creatine Clearance(cc/min)	Dose of Cisplatin
<1.6	>50	75mg/m^2
1.6-2	10-50	60mg/m^2
>2	<10	Delay one week

Other Toxicity

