Patients who develop treatment-related grade 3 non-hematological toxicity (except grade 3 transaminase elevations and nausea or vomiting) should have cisplatin therapy delayed until toxicity has resolved to less than or equal to grade 1 or baseline. Cisplatin will be continued at 60mg/m² for subsequent cycles. For grade 3 nausea, vomiting, or transaminase elevation, treatment will be delayed until toxicity resolves to grade 1 or less, and treatment may resume at 75 mg/m² dose. If any toxicity, including those described above, results in a three week treatment delay, patients will be taken off protocol. Patients with grade 4 non-hematological toxicity attributed to cisplatin will come off study unless exception is given by the Protocol Chair. Prior to retreatment, toxicity must resolve to less than or equal to grade 1 or baseline. For ≥ grade 2 Hgb toxicity, at the treating physician's discretion, dose may be reduced by one dose level in addition to transfusions and/or growth factor support as clinically indicated, with the option to re-escalate at physician's discretion. This should be documented in the medical record.

Table 6-6: Cisplatin Toxicity Management and Dose Modification Summary Table

Toxicity Event	Dose Modification	
Hematologic		
$ANC > 1000/mm^3$	None	
$ANC \geq 500/mm^3$	Delay until >1000/mm ³ and reduce to 60mg/m ²	
	(treat at 75mg/mm ² if initiating GCSF)	
$ANC < 500/mm^3$	Delay until >1000/mm ³ and reduce to 50mg/m ²	
	(treat at 60mg/mm ² if initiating GCSF)	
Grade 3 or 4 toxicity	Withdrawal from study or continue	
after 2 dose reduction		
Plt >100,000/mm ³	None	
Plt >50,000/mm ³	Delay until >75,000/mm ³ and reduce to 60mg/m ²	
$Plt < 50,000/mm^3$	Delay until >75,000/mm ³ and reduce to 50mg/m ²	
C 1 2 4	W'.1.11.C	
Grade 3 or 4 toxicity	Withdrawal from study	
after dose reduction		
Gastrointestinal		
Diarrhea		
Grade 3/4 or	Delay until resolution and reduce to 60mg/m ²	
requiring hospitalization		
Vomiting, Nausea		
Grade 3/4	Delay until ≤grade 1 or has returned to baseline and resume at	
	75mg/m ² or with one dose reduction (Per investigator discretion)	
Transaminases		
Grade 3/4	Delay until ≤grade 2 and with one dose reduction	
Neurological		
Neurosensory		
Grade 0-1	None	
Grade 2	Delay until resolves to ≤grade 1 and resume with one dose reduction	
Grade 3-4	Withdrawal from study	
Ototoxicity		
Tinnitus or	Reduce dose or withdraw from study at investigator discretion	
significant hearing loss		
Nephrotoxicity		
Cr <1.6 mg/dl or	None	

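### Section 6.2 gives conflicting rules for grade 3-4 neurosensory toxicity: its text can be read as restarting cisplatin, and summary Table 6-6 omits the AZD1775-alone option (minor)

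*Combined protocol and SAP*

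**What the plan says.** Section 6.2 addresses grade 3-4 neurosensory toxicity, directly or by a general rule, in five places:

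- **Opening paragraph**, for any reason to stop cisplatin: "If patient needs to discontinue cisplatin therapy, patient can be treated on protocol with AZD1775 monotherapy".
- **Neurotoxicity paragraph**: cisplatin is to be stopped for serious neuropathy, which may worsen even after stopping.
- **Sentence above Table 6-4**: cisplatin is held from grade 2 upward and resumed at a reduced dose at grade 1. Grades 3-4 are not excepted.
- **Table 6-4, grade 3-4 row**: "Withdraw participant from study or continue on AZD1775", followed by the word alone, which the text extraction has moved to the next line.
- **Table 6-6, neurosensory grade 3-4 row**: "Withdrawal from study", with no alternative. The section introduces this table with "Dose delays and modifications are summarized in the toxicity table in Table 6-6".

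No order of precedence is stated.

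Other rules limit any continuation on AZD1775:

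- Section 5.2.2 requires neurosensory toxicity of grade 2 or less before a later cycle starts.
- The Section 6.1 table for other non-hematologic toxicities holds AZD1775 at grade 3 or 4 until below grade 2, then resumes one dose level lower if indicated.
- Under the same table, a patient whose grade 3 or 4 toxicity "does not resolve to ≤ Grade 1 within 3 weeks should discontinue AZD1775, unless approved by the Principle Investigator".
- Section 5.5 ends protocol therapy for "Treatment delay of > 21 days due to toxicity". Section 6.2 adds: "If any toxicity, including those described above, results in a three week treatment delay, patients will be taken off protocol".
- Section 6.2 takes patients with grade 4 non-hematologic toxicity attributed to cisplatin off study unless an exception is given.

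**The concern.** These are operative treatment rules, and a site cannot follow all of them for the same patient. Two separate things are at stake.

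The first is safety. A site reading the sentence above Table 6-4 literally could give cisplatin again after grade 3-4 neuropathy has eased to grade 1. Both tables treat that grade as the end of cisplatin, and the section itself warns that the neuropathy may progress after treatment stops.

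The second is consistency. A site working from the summary table would withdraw a patient whom Table 6-4 allows to stay on the investigational drug. Two sites could therefore treat the same patient differently according to which table they open.

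**Working it through.** The plan has no figure to reproduce here, so the check sets the rules side by side.

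**Step 1. Grade 3-4 neurosensory toxicity in each source**

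| Source in Section 6.2 | Cisplatin | AZD1775 alone |
|---|---|---|
| Opening paragraph | (applies once cisplatin must stop) | allowed |
| Neurotoxicity paragraph | stop if serious | not addressed |
| Sentence above Table 6-4 | hold, then resume at grade 1 | not addressed |
| Table 6-4 | ends | allowed, as one of two outcomes |
| Table 6-6 | ends | not listed; one outcome only |

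**Step 2. Cisplatin.** Both tables end it. The sentence above Table 6-4 alone points the other way, because its grade range has no upper limit. Restricted to grade 2, it agrees with the grade 2 rows of both tables, so grade 2 is very probably what was meant.

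**Step 3. AZD1775 alone.** Table 6-4 lists two outcomes and Table 6-6 lists one. Withdrawal appears in both, so a site that withdraws the patient breaks neither. What is wrong is an omission from the summary.

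**Step 4. Do the other rules remove the option anyway?** They narrow it without closing it. A grade 3 patient who returns to grade 1 within 3 weeks meets the Section 5.2.2 threshold, the Section 6.1 hold rule and the 3-week rule. If dosing has not been delayed to the limit, the patient also meets the delay rules in Sections 5.5 and 6.2. Such a patient may continue on AZD1775 alone under Table 6-4 but is withdrawn under Table 6-6. Slower recovery needs Principal Investigator approval under Section 6.1 and must still respect the delay limits. Grade 4 needs the Section 6.2 exception. Neither the Table 6-4 row nor the Table 6-6 neurosensory row separates grade 3 from grade 4.

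**Step 5. When it would arise.** Section 6.2 puts the usual onset of neuropathy symptoms at 4 to 7 months. At 365.25/12 = 30.4 days per month, 21-day cycles and no delays:

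- 4 months = 122 days; 122/21 = 5.8, so cycle 6.
- 7 months = 213 days; 213/21 = 10.1, so cycle 11.

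This is onset at any grade, not grade 3-4. It suggests only that the question mainly concerns patients on prolonged treatment.

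**Step 6. Could the text extraction explain the omission?** The neurosensory row of Table 6-6 reads as complete. Nearby rows do not: the neutrophil row after two dose reductions breaks off after offering continuation, and a line in the platelet block is garbled. The platelet row also lists only withdrawal, whereas Table 6-3 allows withdrawal or AZD1775 alone after two reductions. It may share the omission, but the damage is close enough that the source PDF must decide.

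**The case against.** The strongest reply is that nothing here forces a wrong action. Withdrawal complies with both tables, Table 6-6 is only a summary, and the general permission for AZD1775 alone stands in the same section shortly before the pointer to that table. That a site would rely on the summary alone is an assumption. All of this stands, and it is why the second part is described as a missing option.

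On cisplatin, the reply is that the hold-and-resume sentence has to be read literally to cause trouble: the sentence before it sends the reader to Table 6-4, and the neurotoxicity paragraph says to stop for serious neuropathy. A careful reader would probably reach the right answer, but a dosing rule should not depend on that.

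The possible loss of table text also stands, and it lowers confidence in the Table 6-6 part. The hold-and-resume conflict does not depend on that row, because Table 6-4 alone contradicts the sentence.

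A reader might infer more than the documents support, in two ways:

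- **That AZD1775 alone is available for at most 21 days.** The 3-week rules set a recovery window and limit treatment delay. Section 6.1 lets the Principal Investigator approve an exception to its resolution rule. Nothing limits how long a recovered patient may then take AZD1775 alone.
- **That the efficacy results or the design's error rates are affected.** Sections 13.2 and 13.4.2 assess response in everyone who receives at least one dose, and the study calendar keeps scanning patients who come off for reasons other than progression. The documents give nothing from which such an effect could be shown.

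**Conclusion.** The inconsistency is real and minor. For one event, Section 6.2 contains a sentence that literally permits cisplatin rechallenge against two tables that end cisplatin, and a summary row with one outcome against a detailed table with two. The cisplatin sentence matters more, because it bears on safety.

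Practical reach is narrow. For AZD1775 alone it is mainly grade 3 patients who recover quickly or have approval, plus grade 4 patients granted an exception. The number cannot be derived, since the documents give no rate of grade 3-4 neuropathy. No effect on objective response rate, progression-free survival or power is claimed.

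The Table 6-6 part assumes that the neurosensory row was read completely from the PDF. The platelet row is a possible further instance, not an established one.

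**What to change.** 1. Limit the hold-and-resume sentence above Table 6-4 to grade 2, and state that cisplatin is permanently discontinued at grade 3-4.
2. After checking the source PDF, reword the Table 6-6 neurosensory row along these lines: *Grade 3-4: discontinue cisplatin; withdraw, or continue on AZD1775 alone under the Section 6.1 non-hematologic rules (hold until below grade 2, resume one dose level lower if indicated, stop if not grade 1 or less within 3 weeks unless approved) and the delay limits in Sections 5.5 and 6.2; grade 4 only with the exception in Section 6.2.* Add the same grade 4 condition to Table 6-4. Citing the Section 6.1 hold rule matters: the Section 5.2.2 threshold alone would seem to allow a restart at grade 2.
3. If the source PDF shows the same omission in the Table 6-6 platelet row, align it with Table 6-3: withdraw, or continue on AZD1775 alone, after two dose reductions.

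The cost is one sentence, one row in each of Tables 6-4 and 6-6, and possibly the platelet row. No visits, scans or patients are added, and every existing safety limit is kept.

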Ototoxicity has been observed in up to 31% of subjects treated with a single dose of cisplatin (50mg/m²) and is manifested by tinnitus and/or hearing loss in the high frequency range (4000 to 8000 Hz). Decreased ability to hear normal conversational tones may occur occasionally. Ototoxicity can be more severe in children than in adults and more frequent and severe with repeated administration. Hearing loss can be unilateral or bilateral and is usually not reversible. During treatment with cisplatin, it is necessary to monitor hearing at each visit as part of a standard physical exam.

Myelosuppression

Myelosuppression occurs in 25 to 30% of subjects treated with cisplatin. The nadirs in circulating platelets and leukocytes occur between days 18 and 23, with most subjects recovering by day 39. Leukopenia and thrombocytopenia are more pronounced at higher doses (>50 mg/m²). Anemia (a decrease in hemoglobin of 2 gm/100ml) occurs at approximately the same frequency and with the same timing as leukopenia and thrombocytopenia.

Neurotoxicity

Cisplatin neurotoxicity is characterized by peripheral neuropathies, which are sensory in nature but can also include motor difficulties such as reduced deep-tendon reflexes and leg weakness. The symptoms usually occur after prolonged therapy (4 to 7 months). Cisplatin therapy should be discontinued when serious neuropathy develops. The neuropathy, however, may progress

further even after discontinuation of treatment.

Hematologic Toxicity

Dose adjustment at the start of a subsequent cycle of therapy will be based on the neutrophil and platelet counts on day 1 of the cycle. ANC must be $\geq 1.0 \times 10^9 / L$ and platelets $\geq 75 \times 10^9 / L$ before the start of each cycle. Treatment should be delayed to allow sufficient time for recovery. Upon recovery, if treatment is resumed, it should be accounting to the guidelines in Table 6-2 with respect to nadir platelet and ANC values for subsequent cycles, except as noted below. A delay in treatment due to hematologic toxicity if more than 3 weeks will result in withdrawal from the study.

The use of colony stimulating factors (filgrastim or pegfilgrastim) is permissible if recommended by the primary treating physician but should be clearly recorded in the medical record and case report form. Prophylactic use of GCSF is not recommended with the first cycle.

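### From cycle 2, platelets of 75 to <100 × 10⁹/L have conflicting cisplatin instructions: full dose on time, full dose after a delay to ≥100, or a cut to 60 mg/m²

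*Combined protocol and SAP*

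**What the plan says.** Four places in the protocol set a platelet rule for cisplatin after cycle 1.

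- **Section 5.2.2 (Subsequent Cycles):** "Platelets must be" at least 75,000/mm³.
- **Section 6.2, Hematologic Toxicity text:** ANC of at least 1.0 and platelets of at least 75 × 10⁹/L are required "before the start of each cycle. Treatment should be delayed to allow sufficient time for recovery". This text bases the adjustment on day 1 counts, then also refers to nadir values.
- **Table 6-3**, titled "Dose Adjustments for Cisplatin Based on Hematologic Values for Preceding Cycle": platelets ≥75 with ANC ≥1.0 give 75 mg/m². An asterisk on all three dose rows, full dose included, leads to a footnote: "Treatment should be delayed until recovery of platelets to" at least 100 × 10⁹/L, with ANC at least 1.0.
- **Table 6-6**, which Section 6.2 presents as the summary of delays and modifications: the row with no modification is "Plt >100,000/mm"³. The next row, for counts above 50,000, reads "Delay until >75,000/mm"³ with reduction to 60 mg/m². Below 50,000 the dose is 50 mg/m² with the same recovery target.

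Two rules limit delay. Section 6.2 states: "A delay in treatment due to hematologic toxicity if more than 3 weeks will result in withdrawal from the study". Section 5.5 lists as a reason to stop protocol therapy: "Treatment delay of > 21 days due to toxicity". Section 6.2 also bars cisplatin re-escalation except where noted. The exceptions it notes concern renal function and hemoglobin.

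**The concern.** A site with a patient at, say, 85 × 10⁹/L can find support in the protocol for three different actions, and no sentence ranks the sources. Table 6-6 is the summary table, so it is likely to be the one consulted in clinic, yet it disagrees with the start criterion in Section 5.2.2.

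What is at stake is consistent dosing and patient safety. Under the footnote, a patient who stays in the 75 to <100 band waits and is removed once the wait passes 3 weeks. Under Section 5.2.2 the same patient is treated on schedule. Under Table 6-6 the patient is treated at a lower dose that cannot be raised again on platelet grounds. The reduction also matters for withdrawal. The Table 6-6 platelet row withdraws a patient for grade 3 or 4 toxicity after dose reduction, without specifying two. Table 6-3 requires two reductions first and offers AZD1775 alone as an alternative.

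**Working it through.** The plan states no figure to reproduce here, so the check applies each rule as written to a range of counts.

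**Inputs**

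- Start threshold ≥75: Section 5.2.2 and Section 6.2 text.
- Dose bands ≥75, ≥50 and <50, giving 75, 60 and 50 mg/m²: Table 6-3.
- Restart threshold ≥100: Table 6-3 footnote.
- Dose bands >100, >50 and <50, giving 75 (no change), 60 and 50 mg/m², with recovery target >75: Table 6-6.
- ANC ≥1.0 throughout, so that platelets alone decide. Full dose is 75 mg/m².

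**Step 1: the same count under every rule**

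| Platelets (× 10⁹/L) | 5.2.2 and 6.2 text: start? | Table 6-3 dose | Table 6-3 footnote: start? | Table 6-6 dose | Table 6-6 recovery target met? |
|---|---|---|---|---|---|
| 60 | no | 60 | no | 60 | no |
| 74 | no | 60 | no | 60 | no |
| 75 | yes | 75 | no | 60 | no |
| 76 | yes | 75 | no | 60 | yes |
| 85 | yes | 75 | no | 60 | yes |
| 99 | yes | 75 | no | 60 | yes |
| 100 | yes | 75 | yes | 60 | yes |
| 101 | yes | 75 | yes | 75 | yes |
| 120 | yes | 75 | yes | 75 | yes |

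At 60 and 74 all rules withhold treatment and both tables give 60 mg/m². At 101 and 120 all rules agree on full dose without delay. Timing and dose both conflict from 75 to <100. At exactly 100 only the dose differs, because Table 6-6 requires more than 100,000. At exactly 75, Table 6-6 also asks for a delay.

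**Step 2: does it help to separate preceding-cycle counts from day 1 counts?**

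Suppose both tables set the dose from the preceding cycle's low point, while the footnote, Section 5.2.2 and the Table 6-6 recovery target govern the day 1 count.

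- Low point 60, day 1 count 85: both tables give 60 mg/m². Section 5.2.2 and Table 6-6 allow treatment; the footnote delays it. The timing conflict remains.
- Low point 85, day 1 count 120: every rule allows treatment. Table 6-3 gives 75 mg/m² and Table 6-6 gives 60 mg/m². The dose conflict remains.

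**Step 3: size for one patient**

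- Dose: 1 − 60/75 = 0.20, a 20% reduction.
- Delay under the footnote: however long platelets take to reach 100. Beyond 21 days, Sections 5.5 and 6.2 end treatment or participation.

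**The case against.** The strongest reply is that the Table 6-3 row and its footnote do not contradict each other. The table is titled for the preceding cycle, so the row can set the dose and the footnote the restart time. That is right, and a reader should not infer a contradiction inside Table 6-3. It leaves the conflict with other text: the restart limit is 100 in the footnote against 75 in Sections 5.2.2 and 6.2 and the Table 6-6 recovery target, and the two tables give different doses.

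A second reply is that the Table 6-6 row for counts above 50,000 might mean 50,000 to 75,000, since a delay to 75,000 is idle above that level. This is possible. The table would then give no instruction for 75,000 to 100,000, so the 20% cut depends on the more natural reading, which runs up to the next row. The conflict over restart timing does not depend on it.

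A third reply is that 100 may be the intended value, since it appears twice in Section 6.2. That stands as a question for the sponsor; it does not make the current text consistent.

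Three stronger inferences are not supported:

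- **Length of the delay.** A reader might size the wait from Section 6.2's statement that most subjects recover by day 39. That describes platelets and leukocytes in general, not the time from 75–99 to 100.
- **Priority between the drugs.** A reader might infer that the cisplatin count tables override the advice in Section 6.1 to modify AZD1775 first. But that advice is a recommendation with stated discretion, and Section 6.2 opens by tying cisplatin reduction for grade 3 or 4 toxicity to attribution to cisplatin.
- **Response rate.** A reader might infer damage to the primary analysis. Nothing in the documents shows this.

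**Conclusion.** The inconsistency is real and should be corrected. From cycle 2, with ANC at least 1.0, a platelet count of 75 to <100 × 10⁹/L can lead to 75 mg/m² on time, 75 mg/m² after a delay to 100, or 60 mg/m² on time. At exactly 75, Table 6-6 adds a delay of its own. Confidence is high for the 75-versus-100 restart conflict, which is explicit in the text. The 75-versus-60 mg/m² conflict also rests on reading the second platelet row of Table 6-6 as reaching up to 100,000.

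The consequence for one patient is a possible 20% dose reduction without platelet-based re-escalation, or a delay that leads to removal if it exceeds 3 weeks. How many patients would fall in the band cannot be stated, because the documents give no distribution of platelet counts. This is a point about dosing consistency and safety; the sample size, decision rule and error rates are untouched.

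**What to change.** 1. In the Table 6-3 footnote, change the platelet recovery value from 100 to 75 × 10⁹/L.
2. In Table 6-6, state the platelet rows as: no modification at ≥75,000; 60 mg/m² for 50,000 to <75,000; 50 mg/m² for <50,000; both reduced doses given after recovery to ≥75,000. This also assigns a count of exactly 50,000, which no row now covers.
3. Align the Table 6-6 platelet withdrawal row with Table 6-3: for grade 3 or 4 recurrence after two reductions, withdraw or give AZD1775 alone.

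The value 75 is proposed because it is the explicit later-cycle start criterion in Sections 5.2.2 and 6.2, the Table 6-3 full-dose limit and the Table 6-6 recovery target. If the sponsor intends 100, Section 5.2.2, the Section 6.2 text, the first row of Table 6-3 and the Table 6-6 recovery targets must change instead.

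The cost is one number in a footnote and the platelet rows of one table. Sample size, decision rule and data collection do not change. The one downside is that the footnote's stricter restart limit is relaxed, so the sponsor should confirm that this is clinically acceptable for the combination.

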CrCl >50 cc/min		
Cr 1.6-2 mg/dl or	50mg/m ²	
CrCl 10-50 cc/min		
Cr>2 mg/dl or	Delay one week	
CrCl <10-cc/min		
Other Toxicity		
Grade 3	Delay until ≤ grade 1 or has returned to baseline and resume at	
	60mg/m^2	
·		

Grade 4	Withdraw from study, unless exception granted by the Principal
	Investigator

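### For grade 4 non-hematologic toxicity attributed to cisplatin and not covered by its own row or subsection, Section 6.2 gives two conflicting re-dosing rules and does not say which governs

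*Combined protocol and SAP*

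**What the plan says.** All the relevant rules are in the protocol, Section 6.2, except where noted.

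- **Non-Hematologic Toxicity paragraph.** The rule opens "For other grade 3 or higher non-hematologic effects" and carves out some events ("with the exception of grade 3 transaminase elevations and nausea or vomiting"). Treatment waits until the toxicity has resolved to baseline or less. It can then restart at 60 mg/m², "if deemed appropriate by the treating physician, for all subsequent cycles".
- **Other Toxicity paragraph.** A near-identical rule is given for grade 3 only: "Patients who develop treatment-related grade 3 non-hematological toxicity (except grade 3 transaminase elevations and nausea or vomiting"). Grade 4 is handled separately: "Patients with grade 4 non-hematological toxicity attributed to cisplatin will come off study unless exception is given by the Protocol Chair". The paragraph adds: "Prior to retreatment, toxicity must resolve to less than or equal to grade 1 or baseline".
- **Table 6-6, Other Toxicity, grade 4.** The entry is "Withdraw from study, unless exception granted by the Principal" Investigator.
- **Table 6-6, named grade 3/4 rows.** Diarrhea ("Delay until resolution and reduce to" 60 mg/m²), nausea/vomiting and transaminases each lead back to cisplatin and mention no exception.
- **Pointers to the tables.** The opening of Section 6 says that delays and modifications follow the tables. Section 6.2 describes Table 6-6 as a summary.

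**The concern.** Take a patient with a grade 4 non-hematologic event attributed to cisplatin that has no row or subsection of its own. Under the first paragraph the default is to resume after recovery, and the treating physician decides. Under the second paragraph and the table the default is to leave the study, and only a named senior role can decide otherwise.

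The plan has chosen an approval step before a patient is re-exposed to cisplatin after grade 4 toxicity. A site that stops reading at the Non-Hematologic Toxicity paragraph can miss that step while following the text. At stake are patient safety and uniform conduct across sites.

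**Working it through.** No arithmetic bears on this beyond the dose ratio 60/75 = 0.80. The check is a side-by-side reading.

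| Feature | Non-Hematologic Toxicity paragraph | Other Toxicity paragraph | Table 6-6, Other Toxicity, grade 4 |
|---|---|---|---|
| Grades | 3 and above | grade 4 sentence | 4 |
| Attribution | not limited | to cisplatin | not stated in the row |
| Default | may resume at 60 mg/m² | off study | off study |
| Who decides | treating physician | Protocol Chair | Principal Investigator |
| Recovery needed | baseline or less | grade 1 or baseline | not stated in the row |

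**Step 1: overlap.** The first paragraph includes grade 4. The second paragraph's grade 4 sentence covers non-hematologic events attributed to cisplatin. Both therefore apply to a grade 4 event that is attributed to cisplatin and has no rule of its own.

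**Step 2: compatibility.** Both can be satisfied by obtaining the exception first and then resuming at 60 mg/m². The first paragraph does not say that an exception is needed, so a site can follow it fully and still breach the second.

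**Step 3: precedence.** The opening of Section 6 directs sites to the tables, and Table 6-6 agrees with the Other Toxicity paragraph. Neither that opening nor the pointer to Table 6-6 says what governs when text and table differ, or when two paragraphs of text differ. The first sentence of Section 6.2 reduces the dose for grade 3 or 4 toxicity attributable to cisplatin without separating grade 4, so it does not settle the matter.

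**Step 4: recovery thresholds.**
- *Other non-hematologic toxicity.* The first paragraph requires baseline or less. The Other Toxicity paragraph and the Table 6-6 grade 3 row accept grade 1 or baseline. Section 5.2.2 requires grade 1 or less. A patient with no such toxicity at baseline who recovers to grade 1 may restart under the last three but not under the first.
- *Transaminases.* The Other Toxicity paragraph requires grade 1 or less after grade 3, and grade 1 or baseline before retreatment after grade 4. Table 6-6 and Section 5.2.2 accept grade 2. A patient who recovers to grade 2 may restart under the table but not under the text.

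**Step 5: effect on the analyses.** Section 13.2 analyzes every patient who starts the regimen. Section 5.6 follows patients to progression or death. Footnote h of the Study Calendar continues imaging every 6 to 9 weeks for those who leave for reasons other than progression. The operating characteristics in Section 13.1 do not depend on this dosing rule.

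**The case against.** The best reply is that the conflict resolves itself. Section 6 sends sites to the tables, Table 6-6 requires the exception, and the Other Toxicity paragraph agrees with it. Two specific statements then stand against one general, permissive sentence. This is a sensible reading and probably the intended one. It is not written, however, and nothing in the permissive paragraph prompts a site to look further.

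A second reply is that other safeguards apply:
- Section 5.2.2 requires recovery.
- Section 5.5 removes patients for unacceptable adverse events and requires immediate notice of life-threatening complications.
- Section 7.2.1 sends SAEs to the Overall PI.
- Section 6.1 asks for consultation with the Principal Investigator when chemotherapy is modified first, and for a joint decision on a second reduction during combination therapy.
- Section 4.1, on registration, asks that issues causing treatment delays be discussed with the Overall PI.

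These reduce the risk. None says whether re-dosing after grade 4 needs an exception.

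Four stronger readings are tempting, and the documents do not support them.
- **The diarrhea, nausea/vomiting and transaminase rows also contradict the grade 4 sentence.** They read naturally as specific rules beside a residual Other Toxicity rule. The scope is not fully clear, because the Other Toxicity paragraph itself sets rules for nausea, vomiting and transaminases. That calls for a clarifying footnote and does not establish a contradiction.
- **Most graded toxicity categories bypass the approval step.** Such a count would have to mix text and table sources. Within Table 6-6 only the three named rows lack an exception step, and the Other Toxicity row has one.
- **The words extending the first paragraph beyond grade 3 are a slip and should be deleted.** The parallel grade 3 rule makes this plausible, but the first paragraph has no attribution limit. It may also be meant for grade 4 events not attributed to cisplatin, and deletion would leave those without a cisplatin rule in the text.
- **Two different people hold the approval power.** Nothing shows that the Protocol Chair and the Principal Investigator are different roles. The labels simply differ.

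**Conclusion.** The conflict is real and narrow. For a grade 4 non-hematologic toxicity that is attributed to cisplatin and has no rule of its own, Section 6.2 both permits resumption at 60 mg/m² on the treating physician's judgment and requires removal unless an exception is granted. No sentence says which governs.

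The conclusion rests on the wording alone. It assumes that the approval step is intended, as the Other Toxicity paragraph and the matching table row both indicate. Without a grade 4 event rate in the documents, the number of affected patients cannot be estimated.

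The consequence is confined to safe and consistent re-dosing. A reader might infer a threat to the response rate or PFS, but the analysis population and continued imaging make any effect on them minor, and the design's operating characteristics are essentially untouched. The gap is still worth closing, because it concerns re-exposure after the most severe non-fatal toxicity grade and the repair is small.

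**What to change.** 1. Keep the Non-Hematologic Toxicity paragraph and add a clause: *after grade 4 toxicity attributed to cisplatin, cisplatin may be resumed only with the exception described under Other Toxicity.* This leaves the paragraph in force for grade 4 events attributed elsewhere.
2. Name the Overall PI as approver in both the Other Toxicity paragraph and the Table 6-6 grade 4 row.
3. Add a footnote to Table 6-6 stating whether the grade 3/4 diarrhea, nausea/vomiting and transaminase rows are exempt from the exception. This is a clinical decision for the Overall PI.
4. Use one recovery threshold for other non-hematologic toxicity, grade 1 or baseline, throughout Section 6.2, and make Section 5.2.2 match.
5. Use one recovery threshold for transaminases in the Other Toxicity paragraph, Table 6-6 and Section 5.2.2. Whether it is grade 1 or grade 2 is also a clinical decision.

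The cost is a few lines of wording in Sections 5.2.2 and 6.2 and two clinical decisions. No procedures, patients or analyses are added.
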